5.2.4 Mentor/Advisor Training

Once mentors /advisors are recruited and deemed eligible they will be scheduled to receive 8- 10 hours of structured virtual training that will be conducted via the Peer Mentor University platform. The virtual training is expected to be completed in no more than 3 weeks (+/- 1 week) from enrollment. Once this virtual training is complete, the mentor / advisor will then be trained on how to access and use the Mentor1to1TM platform to make the required mentoring contacts via telephone (mentors to mentees only) and contacts via SMS messaging (required for all advisor and mentor contacts). SMS messaging can be used as a supplementary resource for mentor to mentee contacts). Mentors will receive an automated

Version 6: 12/22/2022

email from InquisitHealthTM to establish an account which prompts them to proceed with platform training.

Mentor/advisor education material specific to SCD have been created for use with the Mentor1to1TM platform and was prepared in line with evidence-based "Elements of Effective Practice for Mentoring" prepared by the National Mentoring Partnership (Elements for Effective Practice for Mentoring, 2015) following the guidelines provided in Chronic Disease Self-Management (CDSM) program.

Mentor contact via telephone calls (and supplemental SMS messaging) will be monitored and evaluated through the Mentor1to1TM Administrator Platform. Calls between mentors and mentees will be recorded and monitored periodically for quality assurance. All transcripts of mentor—mentee supplemental communication via SMS messaging through the platform will also be available for review for quality assurance by platform administrator.

Mentors will initially be assigned 1 mentee and will complete 1-2 calls with their mentee. These initial calls will be monitored retrospectively by the platform administrators or designee to determine adherence to talking points, quality of mentorship, and to determine any areas of improvement for the mentor. Based on completion of at least four Mentor-Mentee calls, Mentors will be evaluated and assigned additional mentees (up to a maximum of 3) or a plan for improvement in mentoring skills.

- Mentors are expected to have at least 4 calls within a calendar month with mentees during the first 3 months after enrollment.
- Once a total of 12 calls have been completed AND at least 3 months have elapsed since enrollment, mentors are expected to have at least 2 calls per calendar month with mentees until the completion of the study.
- This call frequency will be used for both prospective evaluation and retrospective data to help define potential deviations.

In rare cases, it may be determined that the individual is not a good fit for the role of a mentor. In these cases, the individual will be provided with feedback and will be disenrolled from the platform by the administrator.

- Advisor contact with a mentor via SMS messaging through the platform will be expected to occur at least monthly but may occur more often based on the relationship built between advisor and mentor. All advisor to mentor communication transcripts will be available for review for quality assurance by platform administrator.
- Supplemental mentor / advisor training will be provided virtually and facilitated by the partner CBO and/or will occur during the annual PM conference. Supplemental mentor / advisor training will occur within 6 mo (+/- 1 mo) of initiation of mentoring role (defined as first mentor-mentee or advisor-mentor call).

Annual refresher training will be provided at the PM conferences (either in-person or virtually) to all mentors and advisors.

Version 6: 12/22/2022

Virtual supplemental training will also be available if mentors and advisors are not able to attend the annual PM conferences.

5.2.5 Mentor – Mentee and Advisor – Mentor Communication

Participants will ONLY communicate using the Mentor1to1TM application via a laptop or desktop computer. Each participant will be asked to create a unique password to access the application.

The Mentor1to1TM web-based application software uses two-way line-bridging technology and text messaging to facilitate peer mentoring relationships. The system uses a generic phone number to call the mentor and mentee separately then bridges the line together. Phone numbers are not exchanged between the mentee and mentor, and thus calls are not possible during non-scheduled times. Mentees can respond to phone calls from their mentor through the system generated phone number; they will be prompted to leave a voice message that is delivered to the mentor.

- Mentors are expected to have at least 4 calls within a calendar month with mentees during the first 3 months after enrollment.
- Once a total of 12 calls have been completed AND at least 3 months have elapsed since enrollment, mentors are expected to have at least 2 calls per calendar month with mentees until the completion of the study.
- This call frequency will be used for both prospective evaluation and retrospective data to help define potential deviations.
- Advisors should have contact with mentors monthly.
- Automated phone calls may be generated by Mentor1to1TM platform to the
 mentees if they become hard to reach. Similar alerts are sent to the mentors if they
 have not made their required mentoring contacts and/or have incomplete mentoring
 workbooks after a mentoring call. Structured responses, as appropriate will be sent
 with specific instructions (best time to call, etc.).

5.2.6 Mentor/Advisor Retention

CBOs will be responsible for engaging mentors/advisors in activities such as Community Advisory Board Meetings, community engagement activities and support groups.

- Mentors will be assigned advisors to provide ongoing support and to help reduce mentor burnout.
- Mentors and advisors will be invited to attend an annual mentor conference to
 provide ongoing education and training, improve the mentoring experience, and
 enhance mentor and advisor retention. The annual mentor conference will occur
 every year until the end of the study

5.2.7 Mentor/Advisor Compensation

If permitted under applicable regional laws or regulatory guidelines, mentor/advisors may be reimbursed for time and effort directly related to their role and responsibilities as outlined in the ICF.

5.3 Study Outcome Measures

Study-related surveys will be completed on paper, administered via study-supplied iPad or tablet either within a healthcare setting or sent electronically to the EA-SCD participants via a link

Version 6: 12/22/2022

through REDCap by email. EA-SCD participants will be encouraged to access their ongoing study assessments online, or on paper either at home or during a scheduled study-related clinic visit to optimize study data capture.

5.3.1 PedsQLTM Sickle Cell Disease Module

The **PedsQL**TM Sickle Cell Disease Module 3.0 comprises 6 domains and was derived from qualitative methods involving patient/parent interviews and expert opinion across multiple sites and has been validated for use in the evaluation of SCD specific health related quality of life in research and clinical practice.⁵⁰ This 43-item scale measured on a 5-point Likert-type scale shows excellent feasibility, excellent reliability for the Total Scale Scores (patient self-report $\alpha = 0.95$; parent proxy-report $\alpha = 0.97$), and good reliability for the nine individual scales (patient self-report $\alpha = 0.69$ –0.90; parent proxy-report $\alpha = 0.83$ –0.97).

5.3.2 ASCQ-Me QOC

Adult sickle cell disease care poses significant challenges resulting from poor access to knowledgeable providers and suboptimal treatment in the Emergency departments. The ASCQ-Me quality of care measure was developed to assess the quality of ambulatory and emergency department care experienced by persons living with SCD. The SCD quality of care survey questions were developed and pilot tested in 557 patients using methodology consistent with the Consumer Assessment of Healthcare Providers and Systems survey. This measure is useful in documenting and tracking disparities in quality of care for SCD. ⁵¹

5.3.3 Sickle Cell Transition Intervention Program – Readiness for Transition (TIP-RFT) Assessment

The Sickle Cell **TIP-RFT** instrument was developed to provide a validated SCD specific readiness for transition assessment tool with established reliability for routine use in the clinical domain. ¹⁷ The current TIP-RFT has 4 subscales and 54 items that quantifies knowledge, skills and attitudes necessary for a successful transition from pediatric to adult care. ^{16,52} The domains assessed include knowledge and skills in medical self-care, social support, health benefits, independent living and educational/vocational skills. The TIP-RFT assessment will be used to guide interventions to improve transition readiness and can provide a foundation for future research on other variables that might be associated with transition readiness.

5.3.4 Medical Outcomes Study – Social Support Scale (MOS-SSS)

The Medical Outcomes Study - Social Support Survey (MOS-SSS) was developed as a brief multidimensional social support survey for persons living with chronic illness. ⁵³ MOS-SSS assesses support ranked on a 5-point Likert-type scale along four dimensions, emotional /informational, tangible, affectionate, and positive social interaction, to give an overall functional social support index. ⁵³

5.3.5 Healthcare Transition Feedback Survey for Youth/Young Adult

This survey will provide feedback information on the experiences of youth and young adults with the transition process. This 13-question survey solicits EA-SCD subject-reported feedback on their clinical experiences while in the process of transition from a pediatric SCD clinic to an adult SCD clinic.

Version 6: 12/22/2022

5.3.6 Health Care Transition (HCT) Process Measurement Tool

To determine the level of improvement in a practice with adherence to the Six Core Elements, each pediatric and adult practice will be scored according to whether some or all of the implementation steps have been completed using the HCT Process Measurement Tool developed by GotTransition.org. Scores for each step will vary depending on complexity or importance. Each practice will be scored every six months to determine the degree to which they move closer to adherence to the desired standardized clinical practice pattern.

6. STUDY CALENDAR

6.1 Site Level Quality Improvement Calendar

Site Level Quality Improvement																					
Study Month	Baseline	3	6	9	12	15	18	21	24	27	30	33	36	39	42	45	48	51	54	57	60
Health Care Transition Process Measurement Tools (Pediatric Clinic)	•				•				•	1	Ever	y 6 m	onth	s			•	•	•		•
Health Care Transition Process Measurement Tools (Adult Clinic)	•										Ever	y 6 m	onth	S							
Satisfaction with Transition Services (Provider)	•										Α	nnua	lly								

6.2 Site Level Advisor/Mentor Calendar

Site Level Peer Mentoring																								
Study Month	Screening	Baseline	1	2	3	6	9	12	15	18	21	24	27	30	33	36	39	42	45	48	51	54	57	60
Informed Consent	•																							
Determine Eligibility	•																							
Demographics/Disease Characteristics	•																							
Mentor Role Training	•																							
Advisor/Mentor sign W-8 or W-9 Form	•																							
Distribution of Greenphire Clincard to Advisor/Mentor	•																							
Train on Mentor 1to1 Platforma	•																							
Test Mentor-Mentee call(s) ^b	•																							

Assign Mentee ^c	•					
Supplemental mentor/advisor in person training ^d						
Mentor- Mentee Contacts 4 times a month for first 3 months ^c		•	•	•		
Mentor- Mentee Contacts 2 times per month ^c						Mentor contacts Mentee 2 times per month starting in month 4
Advisor- Mentor contacts monthly					•	Advisor contacts Mentor monthly throughout study
Attend CBO Engagement Activity ^a						Attend bi-annual CBO engagement activities and CAB meetings
Annual Refresher Training ^e	PM Sites Only					Annual beginning in year 2

- a Mentor training must be initiated within 30 days of consent and training must be complete within 60 days of consent.
- b Test or "mock" Mentor -Mentee call(s) will be done through the platform with a DCC designee as part of initial Mentor/Advisor Training.
- c Additional mentees may be added, as appropriate up to a maximum of 3 per mentor at any given time, after completion of at least four Mentor-Mentee calls or DCC approval of additional mentee. Mentors are expected to have at least 4 calls within a calendar month with mentees during the first 3 months after enrollment. Once a total of 12 calls have been completed AND at least 3 months have elapsed since enrollment, mentors are expected to have at least 2 calls per calendar month with mentees until the completion of the study.
- d Supplemental mentor / advisor training at the partner CBO /PM conference will occur within 3 mo +/- 1 mo after mentoring has started. This can also be provided via 1:1 virtual training by the DCC consultant
- e Mentors and advisors will be invited to participate in an annual mentor/advisor conference, but attendance is optional; for those unable to attend, and virtual training will be available.

6.3 EA-SCD Participant Level Assessment Calendar

EA-SCD Participant Level Assessment Calendar																								
Study Month	Screening																							
	All Sites	Peer Mentor Sites Only	Baseline	3	6	9	12	15	18	21	24	27	30	33	36	39	42	45	48	51	54	57	60	Off Study
Eligibility Screening	•																							
Informed Consent / Assent	•																							
Demographics/Disease Characteristics ^a	•																							•
Mentor Matching ^b		● ^g																						
Acute and Ambulatory Care Visit Data Collection ^c			•	•	•	•	•	•	•	•	•	•	•	•	•	•	•	•	•	•	•	•	•	•
Transition Education Intervention Q3			• h	•	•	•	•	•	•	•	•	•	•	•	•	•	•	•	•	•	•	•	•	•
PedsQL-SCD Module			● h		•		•		•		•		•		•		•		•		•		•	•
MOS-SSS			● h		•		•		•		•		•		•		•		•		•		•	•
TIP-RFT			• h		•		•		•		•		•		•		•		•		•		•	•
ASCQ-ME QOC			• h		•		•		•		•		•		•		•		•		•		•	•
Health Care Transition Feedback Survey for Youth/Young			• h				•				•				•				•				•	•
ST3P-Up App	Downloade		Download	•	•	•	•	•	•	•	•	•	•	•	•	•	•	•	•	•	•	•	•	•

- a Demographic information collected at baseline will be re-assessed at end of study for updates and/or changes
- b During screening, EA-SCD subjects are required to provide their day/time availability for peer mentoring calls to facilitate mentor matching. These subjects MUST be matched to a mentor prior to administering baseline surveys
- c Ambulatory and acute care visits will be collected for the preceding 12 months (a month is defined, numerically, as 30.4375 days, and visit windows are based on the date of enrollment). Ambulatory visits will include visits within the healthcare setting, primary care visits, and virtual visits via telephone ONLY. Acute care visits may include, but are not limited to ED, urgent care, day hospitals, infusion centers, and hospital admissions.
- d Study visits will occur with a +/- 4 weeks window for q3mo visits. EA-SCD subject must be seen by their SCD provider during these visits. However, these visits may occur in other locations within the healthcare setting where SCD care is provided or virtually as long as required structured and targeted transition education is provided

Version 6: 12/22/2022

e - ST3P-UP App contains "Who, What, Where, When" Sickle Cell Transition Education Modules that are required for 3-month visits. If app is not available, the education modules are provided to the sites in the QI Change Package and via PowerPoint from the DCC. Alternatively, sites can utilize any standard SCD education module.

- f Patients are encouraged but not required to download the ST3P-UP App. Directions to access the ST3P-UP app and instructions for use will be provided to participants by local site Transition Coordinators. Transition Coordinators are encouraged to use study- provided tablets and/or iPads to facilitate follow-up visit adherence communication and for structured transition education.
- g For PM sites, mentee availability should be captured in the REDCap database at the time of consent. For subjects with delayed enrollment, confirmation of availability should be revisited at the time of Mentor-Mentee matching.
- h Every effort should be made to complete the baseline survey within a healthcare setting but if administration occurs via survey link, this must be provided to the participant within 72 hours from the date of consent (for the STE arm) or from the date of match (for the PM arm). The survey link will expire within 2 weeks of receipt. If the survey remains incomplete after two weeks, please discontinue efforts to contact the participant for completion of the baseline survey.

6.4 Schedule of Assessments

6.4.1 Screening

Subjects who consent for participation and meet the eligibility criteria for enrollment into this study will undergo the following screening assessments (See Section 3.2 for additional details on assessments):

- Collection of baseline demographic and disease characteristics:
 - o Date of birth
 - o Age
 - o Race
 - o Ethnicity
 - Gender
 - o Sickle cell genotype
 - o Zip code of residence (for urban vs rural residency status)
 - o Presence of a sibling, parent, or child (first degree relative) with SCD
 - Academic achievement
 - Disability status
 - o Marital status
 - o Employment status
 - o Living arrangement
 - Household income
- Mentor matching (Peer Mentoring sites only)
 - o Mentee day/time availability information capture
 - o Match facilitated through the Mentor1to1TM platform

6.4.2 Baseline

Subjects who are enrolled into this study will undergo the following baseline assessments (See Section 3.3 for additional details on assessments):

- SCD Provider Clinic Visit
- Historical Healthcare Utilization Data Collection: acute care utilization history (ED/ urgent
- care visits and hospital admissions) and ambulatory visits (SCD provider and Primary Care provider) in the preceding 12 months from the date of enrollment
- TIP-RFT
- MOS-SSS
- ASCQ-Me QOC
- PedsQL-SCD Module
- Health Care Transition Feedback Survey for Youth/Young Adults

6.4.3 Every 3 months after enrollment

• SCD Provider Clinic Visit

A Study Visit will be defined as a touch point with the healthcare team (either in person or virtually) during which the participant receives the structured transition education intervention. The education can be shared with a participant during the virtual visit and providing review or sharing the educational tools via email and requesting a response in review of the information.

- Healthcare Utilization Data Collection: acute care utilization history (ED/urgent care visits and hospital admissions) and ambulatory visits (SCD provider and Primary Care provider) in the preceding 3 months
- "Who, What, Where, When, Sickle Cell Transition Education Module" and/or other sickle cell structured transition education will be shared with the patient either during a SCD clinic visit, at other locations where care is received within the healthcare system or virtually every 3 months to ensure ongoing structured transition education support.

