6.4.6 End of Study

- Demographic update: any change in participant's demographics (e.g. zip code of residence, presence of a sibling, parent or child with SCD, academic achievement, disability status, marital status, employment status, living arrangement, and household income)
- Healthcare Utilization Data Collection: acute care utilization history (ED/ urgent care visits and hospital admissions) and ambulatory care visits (SCD provider and primary care provider) in the preceding 3 months
- TIP-RFT
- MOS-SSS
- ASCO-Me OOC
- PedsOL-SCD Module
- Health Care Transition Feedback Survey for Youth/Young Adults

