9.1.2 Emotional Distress

Some study activities can make participants feel uncomfortable, anxious, and/or emotionally fatigued which are symptoms of emotional distress. If an EA-SCD, mentor, or advisor experiences and reports emotional distress, study activities will be paused until the issue is resolved (see reporting in Section 9.2.2).

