10.2 Sample Size and Accrual

Sample size calculations are based on the primary endpoint of acute care utilization visits per year (at the EA-SCD participant level). Utilizing a randomized cluster design, seven clinical sites will be randomized per arm. The sample size calculation strategy is to calculate the required minimum sample size based on an individual patient randomized design, and then inflate the sample size based on cluster randomized considerations.⁵⁴ A conservative estimate of the average acute care utilization rate for EA-SCD is 6 acute care visits per year based on data for North Carolina reported by the RuSH population surveillance project.⁴ In South Carolina, the acute care utilization rates among 18-30 y with SCD was reported as 7.17 (95% CI 6.34-7.99).55 At Atrium Health (formerly known as Carolinas Healthcare System), 295 EA-SCD had 1972 emergency department visits and 221 hospital admissions in 2015 with an average acute care

utilization rate of 6.82 visits per year. This study is designed to detect a 20% reduction in the number of acute care encounters per year (assuming a base case of 6 encounters). A 20% reduction in acute care utilization is considered clinically significant based on patient partners reporting that 1 less acute care visit a year is meaningful. Based on a two- sided alpha = 0.05significance level, 67 EA-SCD participants per arm would provide approximately 85% power to detect a 20% reduction in the number of acute care utilizations under individual randomization, assuming the number of encounters follows a Poisson distribution for rare events. The sample size will be inflated based on two parameters: the cluster size coefficient of variation and the intra-class correlation (ICC).⁵⁴ The cluster size coefficient of variation observed among the 14 participating clinical sites is 55%. Therefore, the coefficient of variation is assumed to be 60% and the ICC is assumed to be 0.05.⁵⁶ Based on these parameters, a minimum of 183 EA-SCD participants per arm (366 total EA-SCD participants) will retain approximately 85% power. To account for potential missing data and allow for robust evaluation of secondary endpoints the sample size will be increased to a total of 537 EA-SCD participants. It is estimated that this enrollment can be accomplished with an enrollment rate of 35% of the EA-SCD patient population.

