10.3 Endpoints

10.3.1 Definition of Primary Endpoint

Acute care visits will be calculated for each EA-SCD participant as the average number of acute care visits over a24-month period. Acute care visits will also be calculated for each EA-SCD participant as the average number of acute care visits per year over the entire study as a secondary endpoint. Acute care visits may include, but are not limited to hospital admissions, ED, urgent care, day hospital, or infusion center visits. The calculations for these endpoints are below:

$$Months \ on \ study = \frac{(Off \ Study \ Date - Enrollment \ Date)}{30.4375}$$

$$Acute \ care \ visits \ per \ 24 \ months = \frac{Total \ \# \ acute \ care \ visits \ reported \ on \ study}{Months \ on \ study} * 24 \ months$$

$$Acute \ care \ visits \ per \ 12 \ months = \frac{Total \ \# \ acute \ care \ visits \ reported \ on \ study}{Months \ on \ study} * 12 \ months$$

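### Conflicting look-back rules and an enrollment-to-off-study denominator can let uncollected time inside follow-up count as zero acute care visits

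*Combined protocol and SAP*

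**What the plan says.** - **Follow-up look-back.** Section 6.4.3 collects acute care history and "ambulatory visits (SCD provider and Primary Care provider) in the preceding 3 months". Section 6.4.6 repeats this at end of study: "ambulatory care visits (SCD provider and primary care provider) in the preceding 3 months".
- **Visit window.** Note d to the section 6.3 calendar: "Study visits will occur with a +/- 4 weeks window for q3mo visits".
- **A different look-back on the same row.** Note c is attached to the utilization row, which is marked at every time point: "Ambulatory and acute care visits will be collected for the preceding 12 months". It also anchors visit windows to the enrollment date and defines a month as 30.4375 days. Section 6.4.2 uses a 12-month look-back for baseline, so note c is probably meant for baseline, but its words do not say so.
- **Endpoint.** Section 10.3.1: "Acute care visits will be calculated for each EA-SCD participant as the average number of acute care visits over a24-month period". The formula takes visits reported on study, divides by months from enrollment to off study, and scales to 24 or 12 months. Section 10.5.4 defines no other exposure.
- **Missing data.** Section 10.4 analyzes every enrolled participant whatever the missingness. Section 10.5.6 deals with missing covariates and patient-reported outcomes, and has no rule for utilization periods that were not collected.
- **End of follow-up.** Section 7.1 ties the off-study date to where the available utilization data end, after every effort to collect them.

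**The concern.** The numerator and denominator of the primary endpoint can cover different time. The numerator holds only encounters that some look-back reached. The denominator holds every day from enrollment to off study. A day between two collected periods that no look-back reached adds nothing above the line and one day below it. No section states that such a day is a zero; it follows from the formula.

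At stake are the primary rate and the utilization secondaries that section 10.3.2 annualizes in the same way. Under-collection at a similar level in both arms pulls both rates down. Under-collection at different levels moves the rate ratio, and the analysis would report that as an effect of mentoring. With seven sites per arm, open allocation and an ambiguous instruction, differences in how sites apply the look-back could line up with arm. The documents do not show that they would.

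**Working it through.** **The plan's own figure.** Inputs from section 10.2: "two- sided alpha = 0.05significance level", rates 6 and 4.8 visits per year, 85% power, seven sites per arm, cluster-size CV 0.60, ICC 0.05.

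- Individual randomization: n = (1.960 + 1.036)² × (6 + 4.8) / 1.2² = 67.3. Power at 67 is Φ(1.2/√(10.8/67) − 1.96) = 84.8%. This agrees with the plan: "67 EA-SCD participants per arm would provide approximately 85% power".
- Clustered, fixed number of sites: 67 × 0.95 / (1 − 67 × 1.36 × 0.05/7) = 182.3, so 183 per arm, as stated.

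The sample size is not in dispute. It is the base for the power effect below.

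**Timing gaps, if the look-back runs from the actual contact date.**

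- Quarter and look-back: 3 × 30.4375 = 91.3 days each.
- Longest in-window spacing: 91.3 + 56 = 147.3 days, of which 56 days (38%) are uncovered.
- Shortest spacing: 91.3 − 56 = 35.3 days, with 56 days covered twice.
- A contact 28 days late after an on-time one leaves 28 of 119.3 days (23%) uncovered.

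Average over eight contacts, assuming independent timing, uniform within ±28 days:

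- First interval (from enrollment): 28/4 = 7 days uncovered.
- Each of the other seven: 56/6 = 9.33 days.
- Total: 7 + 7 × 9.33 = 72.3 days; 72.3/730.5 = 9.9%. Simulation gave the same mean, with a 95th percentile of 14.8%.

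**Range over assumptions.**

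| Assumption | Share of follow-up uncovered |
|---|---|
| Quarters fixed from enrollment, none missed | 0 |
| 12-month look-back at each contact, no more than three missed in a row | 0 |
| Uniform within ±14 days | about 5% |
| Uniform, 0 to 28 days late only | about 6% |
| Uniform within ±28 days | about 10% |
| Strict early/late alternation (in-window extreme) | 224 days, 29.5% |
| One quarter of eight missed and not recovered, otherwise on time | 91.3/730.5 = 12.5% |
| Two or three such quarters | 25% or 37.5% |

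At 12.5% uncovered, a true rate of 6 reads 6 × 0.875 = 5.25.

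**Equal loss in both arms.** The ratio stays at 0.80. With the design effect held fixed, at the minimum of 183 per arm:

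- 10% loss: Φ(1.08/√(9.72/67) − 1.96) = 80.9%.
- 12.5% loss: Φ(1.05/√(9.45/67) − 1.96) = 79.8%.

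Planned enrollment is 537 in total, above that minimum, so these show the direction and rough cost and do not forecast final power.

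**Unequal loss.** Observed ratio = true ratio × (1 − loss in STE+PM) / (1 − loss in STE).

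- 12.5% lost in STE+PM only: 1.00 becomes 0.875, and 0.80 becomes 0.70.
- 12.5% lost in STE only: 1.00 becomes 1/0.875 = 1.14, and 0.80 becomes 0.91.
- A contrast of 5% against 20% would multiply the ratio by 0.95/0.80 = 1.19 or 0.80/0.95 = 0.84. It is purely illustrative; nothing in the documents suggests those values.

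**The case against.** The strongest reply is that the plan can be read so that no timing gap arises. Note c speaks of 12 months and anchors windows to enrollment. Quarters fixed from enrollment would remove timing gaps, and a 12-month look-back at each contact would also recover up to three consecutive missed contacts. Note d applies to study visits, which section 6.4.3 defines by delivery of the education; utilization collection is a separate item there and a separate calendar row. Section 7.1 foresees utilization data that disagree with attempts to reach the participant, which suggests such data can exist without a contact. Section 8.2 provides monthly monitoring of missingness and endpoint derivation, and section 10.5.2 summarizes missing data on key outcomes.

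Much of this stands. It makes the gap possible rather than certain, and monitoring would help make gaps visible. But monitoring does not change the denominator, fixed quarters do not by themselves recover a missed collection, and a 12-month look-back every quarter could capture one encounter about four times with no stated rule for removing duplicates. Each reading needs an edit.

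Three stronger readings are tempting and not supported:

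- **Exposure keeps running after data stop.** Section 7.1 aligns the off-study date with the end of available utilization data, so the problem is confined largely to interior gaps.
- **A distress pause loses a quarter.** Section 9.1.2 says only that "study activities will be paused until the issue is resolved". It does not mention data collection and does not bar later retrospective collection; section 7.1 names data collection explicitly where it is meant to stop.
- **The study app makes completeness differ by arm.** Section 5.1.4 deploys it to the clinical teams at all sites, so it gives no reason for a difference between arms.

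**Conclusion.** The concern holds in a conditional form. The look-back instructions conflict, no rule recovers a missed quarter or removes double-covered encounters, and the section 10.3.1 formula treats any unrecovered interior period as free of visits. Followed literally, sections 6.4.3 and 10.3.1 can therefore bias the primary rate downward.

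The size is unknown. It is zero under fixed quarters or a 12-month look-back (with the limits on missed contacts shown above), about 10% of follow-up under uniform ±28-day timing with a contact-anchored 3-month look-back, and 12.5% of 24 months for each unrecovered quarter. Equal loss costs a few points of power and leaves the ratio alone. A 12.5% loss in one arm only would turn a true ratio of 1.00 into 0.875 or 1.14. A reader might infer that the trial's result will be biased in a known direction. The documents do not support that: they give neither the amount of loss nor any evidence that it differs by arm.

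**What to change.** 1. Reconcile sections 6.4.3, 6.4.6 and note c: limit the 12-month look-back to baseline, and at every later collection gather encounters since the last date through which utilization data are complete (enrollment if there is none).
2. State that this also applies after a missed contact, so that skipped quarters are recovered.
3. Record each encounter with its date, remove duplicates by date, and record a complete-through date at each collection.
4. In section 10.3.1, use the months covered by utilization collection as exposure, in place of all months from enrollment to off study.
5. Report uncovered time by arm alongside the primary result.

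The cost is short edits to these sections, one date field on the utilization form and slightly more chart review after a missed contact. No visits are added, and the stated 67 and 183 per arm do not change.
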